### ***Histologically Confirmed Disease***

A patient is considered to have histologically confirmed disease if they have no record in their PDMS data that suggests that they did not have histologically confirmed disease. Science considered that the protocol deviation of 'non-histologically confirmed disease' stored in PDMS was more accurate than the tick box on the CRF, as the CRF page is the histological status at the time of collection, but the PDMS system collects information more often. As mentioned, histological disease confirmation information is also collected on the CRF as a tick box, but this information will not be used in the outputs. The reason for using

the PDMS system is that the information on whether a patient had histologically confirmed disease contained in the PDMS system is directly assessed and reviewed by Clinical Science.

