5.4.2 Tumor Tissue Assessment

In metastatic BCC patients who are on study after approval of Study Protocol, version 4.0, archival tissue from a metastatic BCC site will be collected. In metastatic BCC patients who develop tumor progression on vismodegib treatment, a biopsy will be performed if at least one of the progressing lesions is accessible (e.g., skin, superficial mass, or lymph node). One or more biopsies of ONE representative progressing lesion is required per patient.

The archival and progression tumor-tissue samples will be reviewed for tumor histology. In addition, genome-wide technologies to identify somatic gene mutations (e.g., SMO mutations), copy number changes, or gene expression patterns will be carried out on DNA/RNA extracted from these tissues. DNA collected from whole blood will serve as a control for addressing tumor-specific genetic variants.

For sampling procedures and shipping instructions, see the laboratory manual. Assessments will be performed by the Sponsor or a Sponsor-selected vendor.

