8.2.1 Types of Analyses

8.2.1.1 Efficacy Analysis

The efficacy summaries will be presented for the ITT population, which will include all patients enrolled in the study.

The efficacy variable of primary interest for this study is the overall response rate (ORR), as assessed by the Investigator according to RECIST, v1.1. The summary will be

performed on patients with measurable disease at baseline. The best overall response rate (BORR) will be reported. BORR is defined as the number of patients whose best objective response is CR or PR divided by the total number of treated patients in the group for which the BORR is estimated.

Duration of response is the key secondary efficacy variable. It is defined only for the patients whose confirmed best response is CR or PR as the time interval between the date of the earliest qualifying response and the date of PD or death for any cause. For patients who are alive without progression following the qualifying response, duration of response will be censored on the date of last evaluable tumor assessment or last follow-up for progression of disease. This will be done based on Investigator's assessments.

Time to response is defined as the interval between the date of first treatment and the date of first documentation of confirmed CR or PR (whichever occur first). This will be done based on Investigator's assessments.

Progression Free Survival (PFS) is defined as the time interval between the date of the first therapy and the date of progression or death for any causes, whichever occurs first. A patient who died without a reported progression will be considered as an event on the date of death. Patients who have neither progressed nor died will be censored on the date of last evaluable tumor assessment. This will be done based on Investigator's assessments. Patients with non-measurable disease will be assessed for disease progression and included in this summary.

Overall survival (OS) is defined as the time from the date of first treatment to the date of death, regardless of the cause of death. For patients who are alive at the time of analysis, OS time will be censored at the last date the patient was known to be alive. Patients with no post baseline information will be censored at the time of first treatment with vismodegib.

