The best ORRs (confirmed complete and confirmed partial responders) together with the corresponding 95% Pearson-Clopper confidence intervals will be presented. A listing of tumor assessments and best overall response will also be presented.

Estimates for the survivor function for the time-to-event endpoints, including PFS, OS, time to response, and duration of response, will be displayed graphically using Kaplan-Meier (KM) curves. Estimates for the median time to event and the corresponding two-sided 95% confidence interval will be presented with the estimates for the other quartiles and the associated ranges (minimum, maximum). The estimates and KM curves will be presented for the ITT population.

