#### 4. Disease History of Advanced or Metastatic Basal Cell Carcinoma

DMT01
	
Output ID: t_dm_dishis*
 
 
● Analysis Population: Safety-Evaluable Patients
 
● Column Variables: Disease status (Locally Advanced, Metastatic)
 
● Column Totals: Total of non-missing Disease status
 
● Analysis Variables: 
 
1. Diagnosis histologically confirmed               
 
- Yes
 
- No
 
 
 
2. Current disease status               
 
- Metastatic
 
- Locally Advanced                   
 
a) Inoperable
 
b) Surgery Medically Contraindicated                       
 
i) Substantial morbidity and / or deformity
 
ii) Unlikely to be curatively resected
 
iii) Other
 
 
 
 
 
 
 
3. Previously administered radiotherapy               
 
- Yes
 
- No                   
 
a) Contraindicated
 
b) Inappropriate
 
 
 
 
 
4. Measurable Disease Status               
 
- Yes
 
- No
 
 
 
5. Current sites of locally advanced or metastatic disease               
 
- Any Site
 
- Different Disease sites collected on CRF page.
 
 
 
 
 
● Numeric Precision and Formatting of Statistics: Use standard display in the mockup
 

Programming Note:

Refer to CRF Page “Disease History of advanced or metastatic BCC”.

Study MO25616

Page 20 of 104

Output Specifications, Version 1.0

14 September 2015

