## Protocol Violations:

Protocol Violations (PVs) will be taken from the PDMS (Protocol Deviation Management System) and reviewed by Clinical Science. All major Protocol Violations will be summarised and Listed. At the request of the Science team, the Cut-off date should not be used with Violations as the date of the Violations according to the system are the dates that the violation was input, not the date that the violation occurred. Clinical Science reviewed the file to ensure that all correct violations are included and reported.

STREAM Template	Description
MHT01	Output ID: t_pv* 
 
● Analysis Population: Safety
 
● Column Variables: Disease Status (Locally Advanced, Metastatic)
 
● Column Totals: Totals of non-missing Disease Status
 
● Analysis Variables: Total Patients with at least one Deviation, Total number of Inclusion Criteria Violations, Total number of Procedural Violations, Total number of Medication Violations, Total number of Exclusion Criteria Violations
 
● Statistics and Calculation Methods: Use proc freq for individual violations or proc sql for patient counts.
 
● Numeric Precision and Formatting of Statistics: Use standard display in the mockup
 
● Optional Subsetting: For each Category of Violations, include the counts for each individual Violation.
 

PDL01	Output ID: l_pv* 
 
● Analysis Population: Safety
 
● Column Variables: Use Standard STREAM columns
 
● Numeric Precision and Formatting of Statistics: Use standard display in the mockup
 

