## Overall Survival:

TTET01	
Output ID: t_tte_OS_*
 

● Analysis Population: Intent-to-Treat Patients, excluding patients without histologically confirmed BCC. Outputs will be repeated for different population combinations - please see the LoPO for details of these combinations, and the Efficacy Population section for details on populations.

● Column Variables: Disease Status (Locally Advanced, Metastatic)

● Column Totals: Totals of non-missing Disease Status

● Analysis Variables: Overall Survival in Months

● Statistics and Calculation Methods: Use proc freq and proc lifetest.

○ <math>\alpha</math> level for CIs is 2-sided 5%.

○ Use proc lifetest to obtain time to event (Median, Percentiles) information. The 95% confidence interval for the median is calculated using the Brookmeyer & Crowley method.

○ Range, 25th and 75th Percentiles are displayed.

● Numeric Precision and Formatting of Statistics: Use standard display in the mockup

---------------	--

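### The SAP removes patients without histological confirmation of BCC from efficacy outputs that the protocol places on ITT, using a flag with no stated protection from knowledge of outcome

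*SAP*

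**What the plan says.** Protocol Section 8.2.1.1 states: "The efficacy summaries will be presented for the ITT population, which will include all patients enrolled in the study". Response is summarised in patients with measurable disease at baseline, and the best overall response rate is the number of responders "divided by the total number of treated patients in the group for which the BORR is estimated". On the time-to-event endpoints it adds: "The estimates and KM curves will be presented for the ITT population". The section contains no histology restriction.

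The SAP does contain one. The population line for OS reads "Intent-to-Treat Patients, excluding patients without histologically confirmed BCC", and PFS has the same line. Best response, duration of response and time to response combine that exclusion with measurable disease. The Kaplan-Meier plots for duration of response, PFS and OS carry it too.

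The flag has its own entry under General Considerations, titled Histologically Confirmed Disease, with this rule: "A patient is considered to have histologically confirmed disease if they have no record in their PDMS data that suggests that they did not" (that is, did not meet the histology requirement). The CRF tick box on histology is collected but is not to be used in outputs. PDMS is preferred because it is updated more often and because the sponsor's Clinical Science group assesses and reviews it.

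On dates, the Protocol Violations section says "the Cut-off date should not be used with Violations", because PDMS stores when a violation was entered and not when it occurred. Data Cut Derivation describes a general cut applied to the input data.

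The disease-history table (t_dm_dishis) lists "Diagnosis histologically confirmed" and measurable disease status, and its note points to the disease-history CRF page. The General Considerations say the tick boxes for those two items will not be used.

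**The concern.** Two things are wrong on the face of the documents. First, outputs labelled ITT are not the protocol's ITT, and the SAP gives no reason for leaving that population. Second, membership rests on a flag that needs no positive evidence of histology, can change after treatment starts, and is judged by people who can see how patients are doing. An exclusion of that kind is not fixed at baseline. If knowledge of response, progression or death influenced who was queried or logged, the denominators of ORR, PFS and OS would depend on outcome.

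A smaller problem follows from the tick boxes. The histology table (t_histol_SE) takes its counts from PDMS and the disease-history table takes them from the CRF, so the report can show two different counts of the same item. Measurability can likewise disagree with the efficacy denominators.

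**Working it through.** The protocol's own precision figure (Section 8.3) reproduces: the Clopper-Pearson interval for 120/1200 is 8.36% to 11.84%, printed as 8.4%–11.8%. It concerns AE incidence, and nothing below depends on it.

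**Populations side by side**

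| Output | Protocol 8.2.1.1 | SAP |
|---|---|---|
| Response rate | measurable disease, treated | measurable and histology-confirmed |
| Duration of response, time to response | ITT (confirmed responders for duration) | measurable and histology-confirmed |
| PFS, OS | ITT; PFS includes non-measurable disease | histology-confirmed only |
| Kaplan-Meier plots | ITT | histology-confirmed only |

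**Can the flag depend on outcome?** Absence of a record counts as confirmed. Status can change after baseline. The reviewer is the sponsor, and the study is open-label (Protocol Section 6.5). Nothing supplied says the review was blind to outcome or closed before outcomes were seen. The SAP is dated 14 September 2015 and already prints deaths by cohort from a 3 August 2015 snapshot. So dependence is possible. Nothing shows that it occurred.

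**Size.** The number excluded is not given, so this is an illustration.

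- N = 1119 locally advanced and 96 metastatic, from the SAP's Summary of Deaths. The measurable subset is smaller and not given, so these are upper bounds.
- Assumed ORR: 27/63 = 42.9% and 10/33 = 30.3%, from the earlier phase II trial in the protocol's background (Section 1.1.2.2). Responders r: 1119 × 27/63 ≈ 480, and 96 × 10/33 ≈ 29.
- k = 9 exclusions per cohort, an assumption. The t_histol_SE mock-up shows a one-digit placeholder in each cohort's No cell, which is not binding.

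If all k are non-responders, ORR = r/(N − k). If all are responders, ORR = (r − k)/(N − k).

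| Cohort | Full set | 9 non-responders removed | 9 responders removed |
|---|---|---|---|
| Locally advanced | 480/1119 = 42.9% | 480/1110 = 43.2% (+0.3) | 471/1110 = 42.4% (−0.5) |
| Metastatic | 29/96 = 30.2% | 29/87 = 33.3% (+3.1) | 20/87 = 23.0% (−7.2) |

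Other values of k:

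- Metastatic, k = 1: +0.3 or −0.7 point. Metastatic, k = 5: +1.7 or −3.8.
- Locally advanced, k = 56 (5%): +2.3 or −3.0.
- With an assumed 60 measurable metastatic patients, 18/60 = 30.0%. Removing 9 non-responders gives 18/51 = 35.3% (+5.3).

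For scale, the 95% Clopper-Pearson interval for 29/96 is 21.3% to 40.4%.

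For survival, crude metastatic deaths are 18/96 = 18.8%. If 9 excluded patients had all died, the figure is 9/87 = 10.3%. If all were alive, it is 18/87 = 20.7%. These are crude proportions, not Kaplan-Meier estimates.

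**The case against.** Histologically confirmed BCC is the trial's target population, and the exclusion is not hidden. The SAP states it in the population lines, says it will appear in titles and footnotes, counts it in t_histol_SE, and lists major violations. The efficacy tables are also to be repeated for other population combinations listed in the LoPO. That document was not supplied and may include full-ITT versions. Efficacy is secondary, no hypothesis is tested, and the locally advanced shift is small.

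Most of this stands as mitigation. It does not change the main specification, and the three Kaplan-Meier plots are specified only with the exclusion.

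The no-cut-off rule also has a fair defence. Failing a histology entry criterion is a breach at enrolment, so logging it late does not make it a later event.

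Two stronger readings are tempting. A reader might infer that patients who progress are more likely to be found non-BCC, because progression biopsies are examined. Protocol Section 5.4.2 says "The archival and progression tumor-tissue samples will be reviewed for tumor histology", so archival tissue is examined too. The collection covers metastatic patients only, the biopsy needs an accessible lesion, and no text links either review to PDMS. A reader might also infer that PDMS entries made between the 16 March 2015 cut-off and the 3 August 2015 snapshot count. No text dates the PDMS extract, and the SAP does not say whether its general data cut or the violations rule governs the flag.

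**Conclusion.** The departure from the protocol population is established by the text, and so is the conflict over the CRF tick boxes. Outcome dependence is a possibility that the plan leaves open, not a finding. A reader might infer that ORR, PFS and OS are biased upward. The documents do not support a direction: excluding non-responders raises ORR and excluding responders lowers it.

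Under the assumed response rates, with 9 exclusions per cohort and all treated patients as denominator, the effect is negligible in locally advanced disease and could matter in the small metastatic cohort. A smaller measurable subset or more exclusions would enlarge it. The primary safety objective is not affected. The point should be corrected because the remedy is cheap and the true number excluded cannot be judged from the plan.

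**What to change.** 1. Make the protocol population the main analysis: all dosed patients with measurable disease at baseline for ORR, duration of response and time to response (including the duration plot), and all ITT patients for PFS, OS and their Kaplan-Meier plots.
2. Keep the histology-confirmed set as a labelled sensitivity analysis. Have its flag reviewed without reference to outcome and frozen before the efficacy outputs are run.
3. State whether Data Cut Derivation or the Protocol Violations rule governs the flag. Do not apply the clinical cut-off to PDMS entry dates. They are input dates, so an entry failure logged late would drop out and be counted as confirmed.
4. In t_dm_dishis, take the histology and measurability rows from the sources named in General Considerations (PDMS and the target-lesion page).

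The cost of the main analysis is SAP wording and a rerun of existing programs with one filter removed. The sensitivity set also needs a documented review of the flag. The downside is that ORR may differ slightly, because a few patients without confirmed BCC stay in the denominator.

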***Data Cut Derivation***

The input data will have a data-cut applied prior to being stored in a VAD, but will not be stored anywhere as 'cut' raw data. The definition of the data cut is stored in the DAP M3 (Data Cut Spec tab).

## Populations:

### All Subject Population (AP)

The "All Subjects" population is any patient in the study for which their disease status (Locally Advanced or Metastatic, based on the disease history CRF page) is known.

### Enrolled Population (ENR)

The "Enrolled" population is any patient in the study with a recorded Disease status and for whom actual treatment is not recorded as Screen Failure.

### Safety Population (SE)

The "Safety" population is any patient who took at least one dose of study medication according to the dose accountability CRF page. A patient was considered dosed if they had a 'number of capsules taken' record according to the exposure CRF page that wasn't zero or missing.

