18. AEs will be collected on Day 1 of each Cycle and at the follow-up or early termination visit. After informed consent, but prior to initiation of study medications, only SAEs caused by a protocol-mandated intervention will be collected. All AEs (either related to study specific procedures or otherwise) experienced after the patient has signed the Informed Consent form but before they have received study treatment, should be recorded as medical history. All AEs experienced after the patient has started study treatment must be recorded on the AE form of the eCRF, as well as all new AEs experienced during the study and up to 1 month, 3 months, 6 months, 9 months, 12 months after the last dose of study treatment (\pm 5 days). Additionally, non-serious, new AEs considered related to study drug which occur approximately (\pm 5 days) 1 month, 3 months, 6 months, 9 months, 12 months after the last dose of study drug should also be reported. SAEs considered related to study drug should be reported indefinitely.
19. In women of childbearing potential ONLY. At start of amenorrhea/irregular menses, refer to gynecologist or appropriate specialist for assessment of ovaries and uterus, including ultrasound. At resolution of amenorrhea/irregular menses, refer to gynecologist or appropriate specialist for follow-up ultrasound ONLY if there was abnormality identified during previous ultrasound. If amenorrhea/irregular menses recurs, repeat evaluations at start of recurrence as detailed previously. Obtain copy of results from ultrasound and enter any abnormal findings into the CRF.
20. In metastatic BCC patients who develop tumor progression on vismodegib treatment, a biopsy will be performed if at least one of the progressing lesions is accessible, e.g., skin, superficial mass, or lymph node and a whole blood sample will be collected.
21. All concomitant medications used within 14 days before study treatment and up to the end of treatment and approximately (\pm 5 days) 1 month, 3 months, 6 months, 9 months, and 12 months after the last dose of vismodegib at the Safety Follow-Up Visit must be recorded.
22. Study drug vismodegib accountability will be performed at every study visit from Cycle 2 onwards and at the End of Treatment Visit.
23. Patients will keep a diary to record ONLY those occasions when a vismodegib dose was missed. The patient will bring this diary with him/her to each study visit to allow missed doses to be recorded by the Investigator.

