8.2.2 Safety Analysis

The safety variables will be summarized for the safety population, where the safety population will include all patients who received at least one dose of study medication.

If the safety population differs by less than 5 patients from the ITT population, then all summaries will be presented only for the safety population.

AEs, AE Grade 3 or 4, AEs leading to drug interruptions or discontinuation and SAEs

All AEs will be assessed according to the NCI-CTCAE, v4.0 grading system.

The analysis of AEs will focus on treatment-emergent AEs, i.e., AEs occurring on or after the first day of vismodegib administration. Non-treatment-emergent AEs (i.e., those occurring before commencement of study medication) will only be listed.

The incidence, type, and severity of AEs will be summarized according to the primary system organ class (SOC) and within each SOC by the Medical Dictionary for Regulatory Activities (MedDRA) preferred term. Summary tables might be presented for time to first onset of the AE of special interest.

SAEs and AEs leading to drug interruptions or discontinuation will be analyzed similarly. Cause of death will also be summarized and listed.

Premature withdrawal from study and treatment

The number of patients who prematurely discontinued treatment, along with the corresponding reason(s) for discontinuation, will be summarized and listed. The discontinuation from study will be also summarized and listed.

Exposure to Study Medication

The exposure of vismodegib will be summarized by means of descriptive statistics for the cumulative dose and frequency tables (percentages) by Cycles and/or Weeks of treatment. The reason for the dose discontinuation other than disease progression will be also summarized.

Laboratory parameters

Laboratory parameters, hematology, and serum chemistry will be presented in shift tables of NCI-CTCAE grade at baseline versus worst grade during the treatment period. Summary of laboratory parameters will be presented by means, standard deviation, minimum, and maximum. Graphical presentations of the mean value of selected laboratory parameters might be also displayed.

Physical Examination

Physical examination variables will be summarized over time by visit and reported in patient listings.

Vital Signs and ECG

Vital signs and ECG will be summarized over time by means of mean, median, and range (mean and maximum), and will be presented graphically over time.

ECOG PS

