## **Definition of First Dose**

Earliest date of drug dispensed when the amount of drug taken is greater than 0 and the doses are not missed on this date, in case the dose is missed on this date then take the date of the day after the last dose missed amongst the first group of missed doses. A drug is considered 'taken' if there is a non-zero, non-missing 'Taken' record in the subject's Drug Accountability CRF page.

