### **Intent-to-Treat Population (IT)**

The "Intent-to-Treat" population is any patient who took at least one dose of study medication according to the dose accountability CRF page. A patient was considered dosed if they had a 'number of capsules taken' record according to the exposure CRF page that wasn't zero or missing.

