## Output Specifications: Safety Outputs

### Exposure:

Capsules are dispensed to each subject at the time of each visit and are recorded on the CRF. Subjects take a dose of 150 mg daily and fill in any missed dose dates on the Patient Diary, in case of dose missed for any reason. The investigator completes the number of capsules taken between visits on the basis of number of capsules returned by the subject at the next visit.

It is possible for a subject to have taken all the dispensed capsules between two visits and still have a missed dose if there is a delay in scheduling or attending the next visit. Consider the total number of capsules dispensed, taken, and the missed dosing date for daily dose calculation (ie, consider the sum of all dispensed/taken doses).

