## Adverse Events:

### General AE Reporting

Listings will include all AEs unless otherwise specified. A Treatment Emergent AE (TEAE) is defined as an AE that starts on or after the first day of study treatment and within 30 days of last dose (please see General Considerations for definition). Unless otherwise specified, AE and SAE summary tables will be restricted to TEAEs.

In STEVIE, the data collection guidelines require that the same AE is entered multiple times into the database, with a separate record for each change in toxicity grade or Lower Level Term. AEs can be reported using this or a “collapsed” Adverse Events analysis dataset.

The Collapsed Adverse Events dataset is derived by combining records that can be reasonably considered to be referring to a single AE term but with changes in toxicity grade (or lower level term). Records from the original AE dataset are grouped, and each group is represented in the collapsed dataset by a single record. The groups are built up by “chaining” records from the original dataset as follows:

- if the Subject ID, System Organ Class and Preferred Term are the same, and
- either the periods defined by the two AEs’ start and end dates overlap, or the Start Date of the later AE is  $\leq 2$  days after the End Date of the earlier one.

In the single record representing the “collapsed” AE:

- Subject ID, System Organ Class and Preferred Term are copied across from any of the records in the group (these are identical so it doesn’t matter which record these variables come from)
- Severity (i.e. toxicity grade) is taken as the most severe grade in the group
- Start Date is taken as the earliest start date in the group
- End Date, Lower Level Term and Outcome are taken from the record with the latest end date in the group

Examples are given on the next page.

Example of derivation of “collapsed” AEs:

Example 1:

SUBJID	System Organ Class	Preferred Term	Lower Level Term	Severity	Outcome	Start Date	End Date
	GASTROINTESTINAL DISORDERS	DYSPEPSI	DYSPEPSIA	GRADE 2 / MODERATE	RESOLVED		
	GASTROINTESTINAL DISORDERS	DYSPEPSI A	HEART BURN	GRADE 3 / SEVERE	RESOLVED		

Collapsed to:

	GASTROINTESTINAL DISORDERS	DYSPEPSI A	HEART BURN	GRADE 3 / SEVERE	RESOLVED		
--	----------------------------	------------	------------	------------------	----------	--	--

Example 2:

SUBJID	System Organ Class	Preferred Term	Lower Level Term	Severity	Outcome	Start Date	End Date

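### A missing capsules-taken count is read as not dosed, so patients who die or are lost early can leave the SAP's Safety and ITT populations

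*SAP*

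**What the plan says.** Protocol section 8.2.2 states that "the safety population will include all patients who received at least one dose of study medication". Section 8.2.1.1 makes ITT everyone enrolled. Neither carries a capsule-count condition.

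The SAP (Safety Population) admits "any patient who took at least one dose of study medication according to the dose accountability CRF page" and recognises dosing only where there is a capsules-taken "record according to the exposure CRF page that wasn't zero or missing". Under Efficacy Populations, the Intent-to-Treat "population is any patient who took at least one dose of study medication according to the dose accountability CRF page", followed by the same condition. The two SAP populations are therefore identical.

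On how the count arises, the SAP's Exposure section says the investigator completes the number taken "on the basis of number of capsules returned by the subject at the next visit". Protocol Table 1, note 22, says that vismodegib "accountability will be performed at every study visit from Cycle 2 onwards and at the End of Treatment Visit".

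The dose dates rest on the same record. Under Definition of First Dose, drug counts as taken "if there is a non-zero, non-missing 'Taken' record in the subject's Drug Accountability CRF page". Definition of Last Dose needs a return date with an amount taken above zero. A treatment-emergent AE (General AE Reporting) is one that "starts on or after the first day of study treatment and within 30 days of last dose".

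**The concern.** A missing count means that intake is unknown. The SAP turns unknown into none. Early death and early loss to follow-up are obvious reasons why a first bottle would not come back, so the missing counts are unlikely to be random with respect to outcome.

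Safety is the primary objective. The populations that carry the deaths, adverse-event and disposition tables could shed the patients with the earliest bad outcomes. The protocol appears to expect such patients to stay in: section 8.2.1.1 censors OS at first treatment for anyone with no post-baseline information. Under the SAP, a patient last seen at dispensing has no taken record and is not in the OS analysis at all.

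**Working it through.** **1. Reproduce the displayed figures.** From the SAP's Summary of Deaths (Safety-evaluable):
- Patients: 1119 + 96 = 1215. Deaths by reason: 71 + 27 + 12 = 110.
- Mortality: 110/1215 = 9.05% (shown as 9.1%). Locally advanced 92/1119 = 8.22%; metastatic 18/96 = 18.75%.
- Exact 95% Clopper-Pearson interval for 110/1215: 7.50% to 10.81%.

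**2. Follow one patient.** Drug is dispensed on Day 1, the patient dies or is lost in Cycle 1, no bottle returns, and the count is left missing.

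| Output | SAP population | Result |
|---|---|---|
| Deaths, overall AE summary, disposition | Safety | Patient absent |
| All-AE listing, cause-of-death listing | Safety | Patient absent |
| PFS, OS | ITT (same rule) | Patient absent |
| TEAE tables t_ae2 (all, fatal, serious, Grade 3 to 5, discontinuation) | Enrolled | In the denominator; no first- or last-dose date, so events may not be classed as treatment-emergent |
| Best overall response rate | Measurable, histologically confirmed disease | No dosing condition in the programming note |
| Population counts | All with known disease status | Counted under Total Exclusions |

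Protocol section 8.2.2 also has a check on whether Safety and ITT differ by fewer than 5 patients. With identical definitions the difference is always 0, so the check cannot detect anything.

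**3. Size.** The documents do not give the number of dosed patients without a count. Call it k; every value below is an assumption. Mortality with these patients restored is (110 + k)/(1215 + k) if all died and 110/(1215 + k) if none died.

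| k | All died | None died |
|---|---|---|
| 3 | 113/1218 = 9.28% | 110/1218 = 9.03% |
| 5 | 115/1220 = 9.43% | 110/1220 = 9.02% |
| 10 | 120/1225 = 9.80% | 110/1225 = 8.98% |
| 20 | 130/1235 = 10.53% | 110/1235 = 8.91% |

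Restoring the patients raises mortality whenever more than 9.05% of them died. With k = 10, a single death is about neutral (111/1225 = 9.06%).

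The metastatic column is more sensitive: 1 to 3 restored deaths give 19/97 = 19.6% to 21/99 = 21.2%, against 18.75%.

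**4. Dilution in the Enrolled tables.** As a stand-in for fatal TEAEs, take the 71 deaths with adverse event as the primary reason (71/1215 = 5.84%). Suppose k = 10 further patients had fatal AEs. The Enrolled rate would be 71/1225 = 5.80% if those events are not treatment-emergent, and 81/1225 = 6.61% if they are. At k = 20 the figures are 71/1235 = 5.75% and 91/1235 = 7.37%.

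**The case against.** **Other outputs do not depend on the count.** A reader might infer that these patients vanish from every safety and efficacy table. They do not. The Enrolled population has no capsule condition and carries TEAE tables, including fatal and serious events. The response-rate note sets its denominator by disease characteristics, although the separate list of outputs, which was not available, could add a limit. The SAP also counts non-screen-failures excluded from Safety and ITT, lists each patient's population status, and has an output confined to those excluded from Safety. This stands as far as visibility goes. It does not repair the rates: exclusion counts restore no events, and the Enrolled tables rely on dose dates that need the same record.

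**The field need not be blank.** Nothing says the count stays missing when no bottle comes back. The investigator completes it, accountability is also due at End of Treatment, sites keep dispensing and return records, and patients keep a missed-dose diary. Eligibility requires a life expectancy above 12 weeks, so death before the first check should be uncommon. All of this stands: the count may be missing, not must be. But the SAP provides for missing values and gives them the wrong default.

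**The effect is small.** Even k = 20 with all dead (10.53%) lies inside the interval for 110/1215. That bounds the practical impact at those assumed values. It does not make a selection rule tied to outcome acceptable in a study whose primary aim is safety.

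**Conclusion.** The rule is wrong as written. It is narrower than the protocol's safety population and ITT, and it can remove patients because of early death or loss. It should be corrected, but the likely effect on overall rates is modest: at most about 0.2 to 0.7 percentage points of mortality for an assumed 3 to 10 patients who all died (9.28 − 9.05 = 0.23; 9.80 − 9.05 = 0.75 before rounding down), and more in the metastatic column.

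Two stronger readings are not supported. One is that the error can only be reassuring. The rule also removes patients lost alive; if fewer than about 9% of those removed died, restoring them lowers mortality, and adding very short exposures without recorded events would lower AE incidence. A reassuring bias is the likelier direction, because early death is one of the main routes to a missing count, but it is not certain.

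The other is that the displayed 1215 already omits such patients. No enrolled or dispensed total is shown beside it. The figure equals the planned 1200 plus the optional 15 metastatic patients, which gives no sign of material exclusion; since 1200 is approximate, it does not rule exclusion out either.

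**What to change.** Change four SAP definitions together:
- **Safety Population:** treat a patient with drug dispensed and a missing count as dosed, unless there is positive evidence of no intake (taken = 0, or returned = dispensed).
- **Definition of First Dose:** for these patients, use the Day 1 dispensing date. The existing rule already starts from a dispensing date.
- **Definition of Last Dose:** for these patients, state a conservative date, for example the earliest of death, last contact or the end of the dispensed supply. TEAE status, duration and person-years are then defined.
- **Intent-to-Treat Population:** set it to all enrolled patients, as in protocol section 8.2.1.1. Any enrolled patient who never took drug then needs a stated time origin for PFS and OS, since both start at first treatment.

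Footnote the Safety, ITT and Enrolled tables with the number of patients included this way, and how many of them died.

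Dispensing data are already collected, so no new data are needed. The cost is changes to several derivations, not one line: cumulative dose and dose intensity remain unknown for these patients and should be shown as missing. The other downside is that a few patients who never took a capsule may enter the Safety population.
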